5.5. PER PROTOCOL POPULATION [PP]

The PP population includes patients who have at least one baseline and one period 3 value and do not have protocol violations that impact the primary outcome. The patients excluded from the PP population will be identified before database lock (i.e., before unblinding the study team). All protocol deviations and the deviations impacting the primary outcome variable will be documented separately and will be signed off prior to the database lock (i.e., before unblinding the study team). PP population will be used for sensitivity analysis for primary variable.

Document:	\\IEEDC-NAS01A\Biosdata\Mylan\INSULIN_GLARGINE\UXA25824\Biostatistics\Documentation\SAP	Version Number:	Final V1.0
Author:	[name] and [name]	Version Date:	[27JUL2016]

Template No: CS_TP_BS016 – Revision 3
Effective Date: 01May2012

Reference: CS_WI_BS005

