### 1.1 Background and Rationale

Mylan's insulin glargine is being developed globally as a biosimilar to Lantus. In the US, this development is currently following the 505(b)(2) pathway, but will according to the US Food, Drug and Cosmetic (FD&C) Act in the future follow the 351(k) pathway. Hence, criteria for both regulatory pathways will be pursued.

The aim of this extension study is to demonstrate that Mylan's insulin glargine and Lantus® have equivalent safety and efficacy in T1DM patients, when one treatment is substituted with the other. Under the 505(b)(2) pathway this is called "therapeutic equivalence" while under

---

 By March 23, 2020 insulin glargine under section 505 of the FD&C Act shall be deemed to be licensed under section 351 of the Public Health Service (PHS) Act (see section 7002(e)(4) of the BPCI Act) (ref: FDA draft guidance: <http://www.fda.gov/downloads/Drugs/GuidanceComplianceRegulatoryInformation/Guidances/UCM490264.pdf>) as a biosimilar

351(k) this is termed “interchangeability”. Following the transition from 505(b)(2) to 351(k), the clinical equivalence data will be considered to support the interchangeability of Mylan’s insulin glargine and Lantus. Although FDA has not yet issued clear guidelines on interchangeability, interactions with the Agency indicate that in order to show interchangeability between the reference drug and the test drug, the primary endpoint should be assessed for equivalence between two treatment arms; one exposed to continuous use of reference and one exposed to repeated switches, which is defined as at least four (4) periods of adequate durations [three (3) switches or transitions]. Within the 3 switches, the patients will be switched from reference drug to test drug and back again. The Lantus® arm of MYL-GAI-3001 will represent the first of the four periods.

The extension study will be conducted open-label since the 2 formulations have different manufacturers and thus distinct packaging. To avoid bias in the evaluation of the critical endpoints, blinded analysis of immunogenicity and HbA1c data is planned.

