## 6.2 Patient Withdrawal

If, for any reason, a patient discontinues the trial prematurely, the patient may be followed up upon consent and as described in the following withdrawal criteria:

Following are the withdrawal criteria:

1. Withdrawal of consent.
2. For female patients, diagnosis of pregnancy or stated intention to become pregnant. Effort should be made so that the pregnant women still report to the site and are followed until delivery or termination.
3. Repeated protocol non-compliance.
4. At the investigator's discretion (following discussion with the sponsor medical monitor), for safety issues such as severe hypoglycemia or hypoglycemic unawareness. The site should follow-up these patients as per the SCHEDULE OF ACTIVITIES until the 40 week follow-up call.
5. At the investigator's discretion, (following discussion with the sponsor medical monitor), in certain situations such as significant intercurrent illness, hospitalization for surgery, or an SAE. The site should follow-up these patients as per the SCHEDULE OF ACTIVITIES until the 40 week follow-up call.

Investigators must attempt to contact patients who fail to attend scheduled visits (by telephone or other means), to exclude the possibility of an AE being the cause of withdrawal. Should an AE be the cause for withdrawal, the AE must be documented, reported, and followed-up as described in Section 8. If withdrawal was not due to an AE the

Investigator should inquire about the reason for withdrawal. If applicable, request all withdrawn patients to bring back all unused investigational product(s) and return them at the final visit. The attempts to contact patients who fail to attend scheduled visits should be documented in the patient files as should the reasons for withdrawal.

No further evaluations should be performed, and no additional data should be collected if the patient withdraws from the trial and also withdraws consent for disclosure of future information. Data collected before patient withdrawal of consent will be retained and continue to be used, or destroyed if required per local regulation and rules.

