### ***9.2.2. Study Population***

The primary analysis will be based on the mITT population.

- The ITT population includes all randomized patients (including patients who receive incorrect treatment, do not complete the trial or do not comply with the protocol or used prohibited medication) and have baseline (week 0 visit) and at least one post-baseline value. ITT population will be used for secondary variable analyses.
- The mITT population includes all randomized patients (including patients who receive incorrect treatment, do not complete the trial or do not comply with the protocol or used prohibited medication) and have at least one baseline (week 0 visit) HbA1c value and one post-baseline HbA1c value at treatment period 3. The mITT will be used for primary analysis.
- Per Protocol (PP) population. The PP population includes patients who complete at least one baseline and one period 3 values and do not have protocol violations that impact the primary outcome. The subjects excluded from the PP population will be identified before database lock. PP population will be used for sensitivity analysis for primary variable.
- The safety population includes patients who take at least one dose of the trial medication. For safety analyses, patients will be categorized according to the treatment that they actually received. Safety population will be mainly used for safety population.

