14. STUDY TREATMENT NON-COMPLIANCE

Patient will be identified as study treatment non-compliant if the patient meets any following criteria:

- Missing either total meal time insulin or basal insulin doses for 5 consecutive days.
- Missing either total meal time insulin or basal insulin doses for more than 30 accumulative days for completer or more than 20% treatment days for drop-out.
- Taking more than one administration of basal insulin (If multiple injections are required to deliver the required quantity of drug due to logistic reasons, then it is considered as one administration) for 10 days cumulative.
- Taking more than the prescribed basal insulin dose for more than 30 days cumulative.

Number and proportion of patients with noncompliance will summarized along with individual reasons for non-compliance.

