APPENDIX 2. MAJOR PROTOCOL DEVIATIONS

The major protocol deviations are defined in the following table:

PD header as per Protocol	Specific example database
Patient not meeting the following selection criteria (inclusion and exclusion) at screening but still included in the study	
Patients recruited in to the study violating the selection criteria
 
Insulin was initiated only after 6 months of T1DM diagnosis
 
Patient was on basal-bolus insulin therapy for at least 1 year before screening
 
Patient was on once daily Lantus® at stable dose
 
Lab criteria
 
Efficacy criteria - HbA1c
 
Safety criteria - ECG, Eye testing, Safety lab tests, Hb, LDL, TG, ALT, AST, Creatinine, Vital signs, HT
 
Other criteria - C peptide, BMI, infectious samples, drug abuse, Insulin resistance, age

Patient continued in the study despite meeting study discontinuation criteria	
Protocol specified withdrawal criteria
 
Withdrawal of consent
 
Use of prohibited medications [insulin, insulin analogs and other anti-diabetes medications as well as glucocorticoid therapy (oral, intravenous, inhaled or other routes that produce systemic effects)]
 
For female patients, diagnosis of pregnancy or a stated intention to become pregnant.
 
Repeated non-compliance as determined by the investigator in a consolidated overall evaluation of compliance
 
At the investigator's discretion, for safety issues such as severe hypoglycemia or hypoglycemic unawareness.
 
At the investigator's discretion, in certain situations such as significant intercurrent illness, hospitalization for surgery, or an SAE which in the opinion of the investigator warrants withdrawal.

Failure to perform tests or procedures which will impact the interpretation of key endpoints of the study	HbA1c not tested at screening, randomization, 12th and 24th week visit (all missed)
Patient not following treatment regimen mentioned in the protocol	
Patient was not given the assigned IP (instead of test medication, comparator medication was given)
 
Using insulin Glargine that is not IMP and part of the study during the study period

Study procedure issue	
Study completed without signing ICF
 
Sponsor unapproved IP used (temperature or humidity excursion prove.
 
For a patient recruited from Germany, Name, date of birth, or information

Document: \\JEEDC-NAS01A\Biosdata\Mylan\INSULIN_GLARGINE\UXA25824\Biostatistics\Documentation\SAP

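### The per-protocol set does not require the assigned product in each period or at the endpoint HbA1c, so a patient who stopped study drug early under a protocol criterion can remain in it

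*SAP*

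**What the plan says.** The design question is in Protocol 1.1. Two arms are compared, one on continuous reference product and "one exposed to repeated switches, which is defined as at least four (4) periods of adequate durations [three (3) switches or transitions". The Lantus arm of the parent study supplies the first period, so all three switches fall within this trial, at weeks 0, 12 and 24.

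SAP 5.5 defines PP as patients who "have at least one baseline and one period 3 value and do not have protocol violations that impact the primary outcome". Protocol 9.2.2 has the same content: the two values, and patients must "do not have protocol violations that impact the primary outcome". On how exclusions are settled, SAP 5.5 says: "All protocol deviations and the deviations impacting the primary outcome variable will be documented separately and will be signed off prior to the database lock". SAP 15.1.4 then uses PP for the repeat ANCOVA, an MMRM and the multiple-imputation analysis.

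Protocol 6.2, for criteria 4 (safety issues) and 5 (such as intercurrent illness, surgery or an SAE), says: "The site should follow-up these patients as per the SCHEDULE OF ACTIVITIES until the 40 week follow-up call". The Schedule of Activities includes an HbA1c at week 36.

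SAP Appendix 2 lists two major deviations that concern the product taken: "Patient was not given the assigned IP (instead of test medication, comparator medication was given" and "Using insulin Glargine that is not IMP and part of the study during the study period". On the compliance thresholds, SAP 14 says: "Number and proportion of patients with noncompliance will summarized along with individual reasons for non-compliance".

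**The concern.** PP is the only planned set that is narrower than the mITT on grounds of conduct. In an equivalence trial, patients who did not receive the regimen can blur a real difference, and a PP analysis is the usual check on that. Here the regimen is the switching itself. If patients who stopped study drug before the second or third switch stay in PP, no planned analysis isolates patients who went through the switches. Agreement between mITT and PP would then reassure less than it appears to.

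**Working it through.** **1. Following one patient through the rules.** Take a patient in the Mylan sequence who is withdrawn from study drug in period 1 or 2 under criterion 4 or 5 and keeps attending visits.

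| Rule | Source | Outcome |
|---|---|---|
| Baseline HbA1c | SAP 5.5 | Present (week 52 of the parent study) |
| Period 3 HbA1c | SAP 5.5; Schedule of Activities | Present at week 36, off product |
| Not given the assigned product | SAP Appendix 2 | Example is comparator given instead of test; does not describe stopping |
| Non-study glargine or other insulin | SAP Appendix 2; Protocol 5.10 and 12 | Refers to the study or study period; silent on time after a protocol-directed stop |
| Stopping early as a deviation | SAP Appendix 2; Protocol 12 | Not listed; what is listed is continuing despite a withdrawal criterion |
| Minimum exposure or switches made | SAP 5.5; Protocol 9.2.2 | No such rule |

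Nothing clearly removes this patient. Protocol 6.2 does not say outright whether criteria 4 and 5 end treatment or participation. Follow-up on the full visit schedule implies treatment, and the version 2.0 entry in the document history describes it that way.

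Two further points concern Appendix 2. SAP 5.5 does not cite it; SAP 9 does, for the summary of significant violations. Its HbA1c entry names weeks 12 and 24 but not week 36, the primary time point, so it does not fully match the three-period design.

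**2. The plan's own power figure.** Inputs from Protocol 9.1: margin ±0.4, SD 0.61, true difference 0, 69 per arm, 10% without usable data. Two-sided 95% interval from Protocol 9.2.6.

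- Evaluable per arm: 69 × 0.9 ≈ 62.
- SE = 0.61 × √(2/62) = 0.1096.
- Power (normal) = 2Φ(0.4/0.1096 − 1.96) − 1 = 2Φ(1.69) − 1 = 90.9%. The t-based calculation gives 90.4%.

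The stated 90% is reproduced. This sets the scale for the illustration; it says nothing for or against the PP definition.

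**3. Illustration of dilution.** Let a fraction f of the switching arm contribute no product difference. The documents do not give f, so the values below are assumed. A true difference of 0.40 then has expected value δ = 0.40 × (1 − f), and the chance of concluding equivalence is approximately Φ((0.40 − δ)/SE − 1.96). The table gives t-based results with 62 per arm.

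| f (assumed) | Patients (f × 62) | δ | Chance of concluding equivalence |
|---|---|---|---|
| 0 | 0 | 0.40 | 2.5% |
| 5% | 3.1 | 0.38 | 3.8% |
| 10% | 6.2 | 0.36 | 5.5% |
| 15% | 9.3 | 0.34 | 7.8% |

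**4. Power if such patients are removed from PP**, at a true difference of 0. Removing 5%, 10% or 15% from both arms leaves 58, 55 or 52 per arm (rounded down) and gives 87.7%, 85.2% or 82.4% (t-based). Removing them from the Mylan arm only leaves 59, 56 or 53 against 62 and gives 90.0%, 89.0% or 87.8% (normal approximation).

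**The case against.** The strongest reply is that the deviation rules already do most of this work. A type 1 patient off study basal insulin is on some other insulin. Protocol 5.10 prohibits non-study insulins during the study, Protocol 12 treats prohibited medication as a significant deviation, and Appendix 2 lists non-study glargine, all without an exception for time after stopping. Outcome-relevant deviations are to be signed off before lock, and judging them case by case is a recognised approach. Exposure by period, discontinuations, violations and non-compliance are all to be reported.

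Much of this stands. A reader might infer that PP admits any unswitched patient. The documents do not support that: a patient given the wrong product has a listed major deviation and would plausibly be excluded. Nor is non-compliance without consequence, since repeated non-compliance is a withdrawal criterion and continuing such a patient is a listed deviation.

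What the reply does not settle is the patient who stopped as the protocol provides. Treating the insulin that patient then takes as a violation is one possible reading, but no text says so. The case is left to a judgement that SAP 5.5 places before unblinding of the study team, in a trial where investigators and patients know the assignment (Protocol 3.5).

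Three further inferences fail:

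- The 10% in Protocol 9.1 is not evidence for f. Those patients lack a baseline or last-period HbA1c, so they are outside both mITT and PP.
- A difference diluted to 0.40 would not usually pass. The whole interval must lie within ±0.4, and its half-width is about 1.98 × 0.1096 = 0.22, so an estimate above about 0.18 fails.
- The bias need not run toward equivalence. Patients withdrawn for severe hypoglycemia, illness or an SAE may have a higher or lower HbA1c afterwards.

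**Conclusion.** The point holds for patients who stop study drug under criterion 4 or 5 and still provide a period 3 HbA1c. As written, PP can include them although they did not complete the switches and were off product at the endpoint. It does not hold for wrong-product patients, whom Appendix 2 covers.

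The effect is on how much the PP analyses can say about three switches, not on the mITT primary result. Its size cannot be derived from the documents. The 3.8% to 7.8% range rests on an assumed f of 5% to 15%, affected patients who behave on average like the Lantus arm, 62 per arm, SD 0.61 and no covariate adjustment. If off-product HbA1c moves otherwise, the bias could go either way, and PP would still not measure the effect of the switching regimen. The gap is worth closing because the change is cheap and PP is the only conduct-restricted set.

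**What to change.** Before database lock, amend SAP 5.5 so that PP requires:

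- (a) the assigned product received in each of periods 1, 2 and 3 (all three switches in the Mylan sequence, Lantus throughout in the Lantus sequence);
- (b) the period 3 HbA1c used as endpoint taken while on the assigned product.

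In the same section, state which Appendix 2 deviations exclude from PP. Use the SAP 14 criteria only where the lapse bears on the period 3 HbA1c. A blanket exclusion would remove patients for an early or mealtime-only lapse that need not affect week 36, and would depart from PP's own test of impact on the primary outcome. Report per arm how many mITT patients fail (a) or (b). Leave the mITT primary as it is.

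The cost is SAP wording and programming from dosing and accountability data already scheduled. Accountability runs to week 36. The diary dose record is given as weeks 0 to 24 in Protocol 7.2.5 but 0 to 36 in SAP 15.2.1.4, so accountability is the safer source for period 3. The downsides are a smaller PP set, a wider sensitivity interval (power as in step 4 of the working) and possible selection from exclusions made after randomisation. The last is why this belongs in the sensitivity analysis only.

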6. GENERAL CONSIDERATIONS

6.1. REFERENCE START DATE AND STUDY DAY

Study Day will be calculated from the reference start date, and will be used to show start/ stop day of assessments and events.

Reference start date is defined as the day of first dose of study medication (Day 1 is the day of the first dose of study medication in extension study), and will appear in every listing where an assessment date or event date appears.

If the date of the event is on or after the reference date then:

Study Day = (date of event – reference date) + 1.

If the date of the event is prior to the reference date then:

Study Day = (date of event – reference date).

In the situation where the event date is partial or missing, Study Day, and any corresponding durations will appear partial or missing in the listings.

6.2. BASELINE

Unless otherwise specified, baseline is visit 1, which includes the post study measurements from week 52 of the main study MYL-GAI-3001 and assessment prior to receiving randomized treatment sequence group (including unscheduled assessments) in extension study. In the case where the last non-missing measurement and the randomized treatment sequence group start date coincide, that measurement will be considered pre-baseline, but Adverse Events (AEs) and medications commencing on the randomized treatment sequence group start date will be considered post-baseline.

6.3. RETESTS, UNSCHEDULED VISITS AND EARLY TERMINATION DATA

In general, for by-visit summaries, data recorded at the nominal visit will be presented. Unscheduled measurements will not be included in by-visit summaries, but will contribute to the best/ worst case value where required (e.g. shift table).

In the case of a retest (same visit number assigned), the earliest available measurement for that visit will be used for by-visit summaries.

Early termination data will be mapped to the next available visit number for by-visit summaries.

Listings will include scheduled, unscheduled, retest, and early discontinuation data.

Document:	\\JEEDC-NAS01A\Biosdata\Mylan\INSULIN_GLARGINE\UXA25824\Biostatistics\Documentation\SAP	Version Number:	Final V1.0
Author:	[name] and [name]	Version Date:	[27JUL2016]

Template No: CS_TP_BS016 – Revision 3
Effective Date: 01May2012

Reference: CS_WI_BS005

Copyright © 2012 Quintiles Transnational Corp. All rights reserved.

The contents of this document are confidential and proprietary to Quintiles Transnational Corp. Unauthorized use, disclosure or reproduction is strictly prohibited.

6.4. WINDOWING CONVENTIONS

Allowed time window for each visit will be performed as mentioned in protocol **Schedule of Activities** (page numbers 18 and 19).

6.5. STATISTICAL TESTS

All tests of treatment effects will be conducted at a two-sided alpha level of 0.05 or with 2-sided 95% confidence intervals, unless otherwise specified.

6.6. COMMON CALCULATIONS

For quantitative measurements, change from baseline will be calculated as: Test Value at Visit X – Baseline Value

6.7. SOFTWARE VERSION

All analyses will be conducted using SAS version 9.2 or higher.

7. STATISTICAL CONSIDERATIONS

7.1. ADJUSTMENTS FOR COVARIATES AND FACTORS TO BE INCLUDED IN ANALYSES

The following covariates and factors are used in the analyses. For details of their inclusion in the models, see the specific analysis section.

- Geographical Region (Categories North America/ Europe)
- Baseline value (Continuous Variable)

7.2. MULTICENTER STUDIES

This study will be conducted by multiple investigators at multiple centers globally. Randomization to treatment sequence arms is stratified by region.

Geographical region will be categorized as follows:

Geographic Region	Country
North America	United States of America, Canada

Document: \\IEEDC-NAS01A\Biosdata\Mylan\INSULIN_GLARGINE\UXA25824\Biostatistics\Documentation\SAP
Author: [name] and [name] Version Number: Final V1.0
Version Date: [27JUL2016]

Template No: CS_TP_BS016 – Revision 3
Effective Date: 01May2012

Reference: CS_WI_BS005

Copyright © 2012 Quintiles Transnational Corp. All rights reserved.

The contents of this document are confidential and proprietary to Quintiles Transnational Corp. Unauthorized use, disclosure or reproduction is strictly prohibited.

Europe	Latvia, Estonia, Slovakia, Czech Republic, Hungary, Germany
--------	---

A term for treatment by region interaction will not be included in the primary analysis model, however, a sensitivity analysis, based on the primary model but including a term for treatment sequence by region interaction, will be performed.

7.3. MISSING DATA

Missing primary and secondary efficacy and safety analysis data will be not imputed except when week 36 HbA1c data is missing due to early discontinuation, exit measurement of that period will be used for endpoint. In addition, for sensitivity analysis of multiple imputation method, if missing values occur in more than 10% of the patients for HbA1C values, then monotone regression for multiple imputations will be used.

